7.5. Handling of Dropouts or Missing Data

Handling of missing concentration data will be detailed in PK analysis plan and/or report. Missing data for adverse events, laboratory test will not be imputed. Last observation carried forward (LOCF) will be used to impute efficacy endpoints.

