7.10 Visit 7 (Study Week 12)

The following tests and evaluations will be performed:

- Review medical history for events since last visit;
- Review concomitant meds since last visit;
- Review voiding diaries;
- Participants complete KHQ and SF-12 (QoL), global assessment of disease state and response to treatment;
- Participants complete ICIQ-SF;
- Physical examination including urogenital examination and vital signs;
- Obtain urine and blood specimens for analysis of *hSlo* cDNA with PCR;
- Obtain blood for the following laboratory determinations:
 - Hematology: Complete Blood Count (CBC) with differential, platelet count, sedimentation rate (sed rate), PTT and PT.
 - Fasting chemistry: Blood Urea Nitrogen (BUN), creatinine, electrolytes (Na⁺, K⁺, Ca⁺⁺, Mg⁺⁺, CO₂, Cl), albumin, alkaline phosphatase, ALT, AST, GGT, LDH, total bilirubin, total protein, C-reactive protein (CRP), CPK, antinuclear antibody (ANA), and glucose.
- Obtain urine for routine urine analysis: microscopic RBC and WBC, protein, glucose, nitrites, pH, and specific gravity;
- Collect and weigh pads used for 72 hours;
- Provide patient with diary materials;
- Instruct the participant to complete daily voiding diaries and return with results at next visit including pads used for 72 hours prior to that visit (and clean pad to be used as a baseline). The site must call participants at least 7-8 days prior to next scheduled visit to remind patient to complete the diaries for 7 days prior to next visit.

7.11 Visit 8 (Study Week 24) or Exit Visit:

The following tests and evaluations will be performed:

- Review medical history for events since last visit;
- Review concomitant meds since last visit;
- Review voiding diaries;
- Participants complete KHQ and SF-12 (QoL), global assessment of disease state and response to treatment;
- Participants complete ICIQ-SF;
- Physical examination including urogenital examination and vital signs (and weight);
- Electrocardiogram;
- Bladder scan for residual volume and bladder capacity (prior to catheterization);
- Perform cystometry;
- Obtain blood for the following laboratory determinations:
 - Hematology: Complete Blood Count (CBC) with differential, platelet count, sedimentation rate (sed rate), PTT and PT.

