8.2 List of withdrawal criteria

WITHDRAWAL OF A PARTICIPANT DUE TO ANY SERIOUS ADVERSE EVENT REQUIRES THAT THE SPONSOR BE INFORMED **WITHIN ONE WORKING DAY AFTER THE INVESTIGATOR IS MADE AWARE OF THE EVENT.** PLEASE REFER TO SECTION 9, ADVERSE EVENT REPORTING.

Those participants who do not complete the study for any reason will be considered a premature termination. The procedures for the Visit 8 should be completed when a participant discontinues the study.

- **Adverse Events:**

Participants with adverse events, severe enough to necessitate discontinuation of study drug administration as judged by the investigator.

The treating physician should take appropriate clinical action. The condition should be treated according to routines of the clinic. The participant should be followed up regarding the safety measurements stated in the protocol.

- **Consent Withdrawn:** participant decided to withdraw from the study for non-medical reasons that the investigator/patient deemed sufficient to warrant premature termination.
- **Lost to Follow-up:** participant failed to return for required visits and cannot be contacted. Reasonable effort should be made by the investigator to contact any patient who fails to return to the clinic for a scheduled visit in order to complete assessments and retrieve any outstanding data. All such efforts should be documented in the source notes.
- **Sponsor/Investigator Decision:** A participant may be withdrawn at any time at the discretion of the investigator.

If a participant discontinues from the study, she should always be contacted in order to give the investigator information about the reason(s) for discontinuation and any adverse events. Whenever possible, the patient should return for a clinic visit at the time of or soon after discontinuation. Any outstanding data or study medication should be collected. Adverse events should be followed up.

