4.4.2. Outcome Assessments

OAB / DO Objective Assessment: Cystometry

Clinical assessment of the efficacy hypothesis that *hMaxi-K* will reduce detrusor overactivity. Detrusor overactivity will be assessed with two standardized, sitting position, saline cystometries followed by pressure flow studies (see Protocol Appendix D). Every attempt should be made to perform the studies at the same time of day and in the same way for each participant. Studies are to be completed at V1A (screening), V5 (4 weeks post dosing with study drug) and V8 (or Final Visit). An over-reader will interpret the results as well as the investigator, however, the over reader's interpretation will take priority for the analysis.

Clinical Evaluation of OAB / DO

Voiding Diary

Clinical signs and symptoms of OAB / DO will be determined by a daily voiding diary. The participants must complete the diaries for the 7 days prior to the Baseline Visit (Visit 2), and for 7 days prior to Visits 3 to 8. The participants will also complete the diaries prior to Visit 1A to test for compliance and evaluate for some inclusion criteria. The site will contact the participant 7 to 8 days prior to the scheduled visit (Visits 2 to 8) to remind the participant to complete the diary. The daily voiding diary will collect standard bladder function and frequency parameters including frequency of micturitions, volume voided and urgency (1 or greater on scale) and incontinence (accidents) episodes. The urgency questionnaire is a 4 point scale with 1 to 4 indicating the presence of urgency. See Protocol Appendix F.

Pad Test

Each participant will record their use of any pads/panty liners (eg, Poise[®] pads or Depends[®], etc.) in their diary. The participant will bring in pads/diapers worn prior to Visit 1A and for the three days prior to Visit 2 (as well as a new pad/diaper to use as a baseline) and for the 3 days prior to all subsequent visits (Visits 3 to V8). Used pads/diapers will be stored in a plastic bag provided by the site and weighed upon receipt and compared to the clean pad. All pads/diapers used by the participants for the 7 days prior to each visit, will be counted by the participants and entered in the voiding diary by them.

King Health Questionnaire and Assessment of Disease State/Treatment

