6. ANALYSIS POPULATIONS

Safety Analysis Population: For safety analyses, the Safety Population will be used. This population consists of subjects who have been dosed including partial/incomplete doses.

Efficacy Population will be used to for efficacy analyses. This population include subjects who are dosed and have at least one post-dose efficacy assessment.

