9. EFFICACY ANALYSES

9.1. Primary Efficacy Analyses

The per participant listing for voiding diary (Dispense Daily Voiding Diary/Urgency Questionnaire) will be presented in Listing 16.2.6.1. The cystometry overread parameters will be presented in Listings 16.2.6.2.1 and 16.2.6.2.2, and in Listings 16.2.6.2.3 through 16.2.6.2.5 for site investigator read. The bladder scan per subject will be detailed in Listing 16.2.6.3 and the pad test in Listing 16.2.6.4. The QoL survey will be presented in two listings with King's Health Questionnaire (KHQ) in Listing 16.2.6.5.1 and SF-12 in Listing 16.2.6.5.2. Per participant assessment of disease and response to treatment will be detailed in Listing 16.2.6.6. Also, participant response to International Consultation on Incontinence Questionnaire (ICIQ) Short Form will be presented in Listing 16.2.6.7. The primary efficacy result, the reduction of the number of voids per day compared to placebo using voiding diary data, will be presented in Table 14.2.1.1. Assuming the number of voids follows a normal distribution, we will test whether there is significantly more reduction in the treatment group at each time point, where there are difference between treatment groups for the pooled *h*Max-K group vs. the placebo group using linear mixed effect model adjusting for the clustering effect by each individual with treatment, time and interaction of time and treatment. We will also present the summary statistics of voiding at each visit and change from baseline at each postdose time point. Difference in change and corresponding 95% confidence interval from baseline for each treatment group vs. placebo and 24,000 µg vs. 16,000 µg will also be presented in Table 14.2.1.1.

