P_{abd} (cm H ₂ O)	Maximum abdominal pressure during any contraction	MAXIMUM abdominal pressure during ANY contraction. This will assess the abdominal straining component to voiding ^{c,d}
a To be analyzed b This is done by overreader, but not the sites c Listing only; not analyzed d Done by site only e Detrusor pressure at first involuntary contraction is called “ Detrusor Pressure ” for sites on eCRF. f Maximum detrusor pressure at ANY contraction is called “ Maximum Detrusor Pressure ” for sites on eCRF.		

The Cystometry overread parameters will be used for objective evaluation analyses. Binary outcomes will be estimated using generalized estimating equation (GEE) model with binary distribution and a logistic link clustered by participant. The parameters that can be treated as continuous variables will be analyzed similarly to the primary efficacy endpoint using linear mixed effect model adjusting for clustering effect by participants.

The mapping of the cystometry parameters that will be analyzed and the corresponding tables that will be used to present the results are shown in [Table 3](#).

Table 3: Cystometry Parameter Analysis Endpoints and Tables that will present the Analysis Results

1) Detrusor overactivity ≥ 5 cm H ₂ O (yes/no- INCLUSION CRITERIA)	Table 14.2.4.1: Cystometry Overread: Change in the Presence and Absence of Detrusor Overactivity (DO)
2) Volume at first desire to void	Table 14.2.4.2: Cystometry Overread: Change of Volume at First Desire to Void (mL)
3) Detrusor pressure at beginning of voiding (prior to onset of first contraction (either volitional or involuntary))	Table 14.2.4.3: Cystometry Overread: Change from Baseline for Detrusor Pressure Prior To Onset of First Contraction (Either Volitional Or Involuntary) (cm H ₂ O)
4) Volume at first involuntary contraction; if detrusor overactivity (DO) present-Not applicable if no DO present	Table 14.2.4.4: Cystometry Overread: Change from Baseline for Volume of First Involuntary Detrusor Contraction (mL) in Presence of Detrusor Overactivity
5) Maximum detrusor pressure at FIRST contraction	Table 14.2.4.5: Cystometry Overread: Change of Maximum Detrusor Pressure at FIRST Contraction (Voluntary or Involuntary) (cm H ₂ O)

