KHQ scores for the nine domains will be calculated according to the Protocol Appendix. Change from baseline at each time point for the QoL endpoints will be analyzed and presented similarly to primary efficacy endpoint using linear mixed effect models in Tables 14.2.5.

We will tabulate the frequency and proportion of participant perception of response to treatment by time point and treatment group in Table 14.2.6. The Cochran–Armitage test will be used whether the treatment group has better response.

Exploratory Figures may also be generated for change from baseline by treatment for frequency of urination (Figure 14.2.1), volume of urination per day, number of incontinences episodes, and urgency (Figures 14.2.1.1 through 14.2.1.3) from voiding diary data, number of detrusor contractions (Figures 14.2.2). The contents and layout of the figure will be similar to that displayed in Figure 14.2, a figure for illustrative purpose only. Possibly other variables may be presented as figures if the data justifies the presentation.

Participant cystometry detailed measures from both overreader and site Investigators will be displayed in Listings 16.2.6.2.1 through 16.2.6.2.5.

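### LOCF is the only missing-data rule for efficacy, although the main mixed model can run without it under missing-at-random; separately, that model has no baseline covariate, which usually costs precision

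*SAP*

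**What the plan says.** SAP 7.5 leaves missing adverse-event and laboratory data unimputed. For efficacy its whole rule is "Last observation carried forward (LOCF) will be used to impute efficacy endpoints". No endpoint is excepted, no missingness assumption is stated, and no sensitivity analysis is planned.

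SAP 9.1 analyses voids per day, as change from baseline, with a "linear mixed effect model adjusting for the clustering effect by each individual with treatment, time and interaction of time and treatment". Other continuous endpoints follow the same model. For detrusor overactivity (DO), SAP 9.2 says: "Binary outcomes will be estimated using generalized estimating equation (GEE) model with binary distribution and a logistic link clustered by participant". For response to treatment, a Cochran–Armitage "test will be used whether the treatment group has better response".

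Baseline as a covariate appears only in SAP 9.3, as an ANCOVA option in the exploratory week-by-week analysis. SAP 7.7 names only time, and only as a possibility.

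Four other rules bear on the point:

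- The Efficacy Population is "subjects who are dosed and have at least one post-dose efficacy assessment" (SAP 6), so early leavers stay in.
- SAP 4.2.2 allows up to three replacements per dose for participants who leave before about one month. Nothing removes the replaced participant from the efficacy analysis.
- Protocol 8.2 says: "The procedures for the Visit 8 should be completed when a participant discontinues the study". The Visit 8 heading in the protocol reads "Visit 8 (Study Week 24) or Exit Visit". No SAP rule says at which week exit data are analysed.
- On cystometry, SAP 4.4.2 says: "Studies are to be completed at V1A (screening), V5 (4 weeks post dosing with study drug) and V8 (or Final Visit".

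**The concern.** A likelihood-based mixed model can use a participant's observed visits and needs no filled-in values under MAR. Filling them first makes the model treat a copied early value as a real later measurement. If the effect fades after someone leaves, LOCF preserves an effect that has gone. If it builds, LOCF hides part of it. In a trial this small, a few carried values can shift the week-24 picture of activity.

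Dropout is a realistic possibility. In the earlier OAB trial (Protocol 1.4.2), 3 of 10 participants at 5000 µg left early to seek other OAB treatment, against 0 of 6 at 10000 µg and 0 of 5 on placebo. The protocol also allows, in general terms, that efficacy may vary over time (Protocol 1.2 Overview).

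The baseline issue is separate. Subtracting baseline is usually less precise than adjusting for it, and precision is scarce at 12 vs 6.

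**Working it through.** **Inputs from the documents.** 12 active and 6 placebo (SAP 3.2). SD 2.5 and placebo mean 10.0 (SAP 5). Diary visits at weeks 1, 2, 4, 8, 12 and 24 (SAP Table 1). A 30% reduction from 10.0 is 3.0 voids/day. **Assumptions, because the documents give no values:** dropout number and timing, the time course of effect, and the correlation rho between visits.

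**The plan's own figure.** SAP 5 gives power 0.80251 for 9 vs 10, means 10.0 vs 6.6, SD 2.5. A two-sided noncentral t with 17 df gives 0.797, so SD 2.5 is used as the plan uses it. The plan gives no figure for missing data.

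**LOCF bias, random dropout.** With dropout fractions d_A and d_P and arm means μ:

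bias = d_A[μ_A(last) − μ_A(24)] − d_P[μ_P(last) − μ_P(24)]

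Negative bias overstates benefit. Take d_A = 2/12, d_P = 0, last visit week 8:

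- waned (−3 at week 8, 0 at week 24): (2/12)(−3 − 0) = −0.50
- constant (−3 throughout): 0
- linear (−1 at week 8, −3 at week 24): (2/12)(−1 + 3) = +0.33
- late (0 at week 8, −3 at week 24): (2/12)(0 + 3) = +0.50

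Unequal dropout with a changing effect is not required. Equal 15% dropout with an effect moving from −1.7 to −3.4 gives 0.15 × 1.7 = +0.26. Dropout of 30% vs 0% with a constant effect and a further drift of −1 void/day in both arms gives 0.30 × 1 = +0.30.

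**Simulation at trial size** (12 vs 6, two active leavers after week 8, rho 0.5, equal correlation; SE of the week-24 difference about 1.27). Entries are LOCF bias in voids/day:

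| Who leaves | waned | constant | linear | late | Observed-data model |
|---|---|---|---|---|---|
| Random two | −0.52 | −0.03 | +0.31 | +0.49 | within 0.03 of 0 |
| Worst two at week 8 | −0.23 | +0.29 | +0.61 | +0.84 | within 0.05 of 0 |
| Worst two at week 24 | −0.79 | −0.31 | +0.03 | +0.24 | −0.42, −0.44, −0.43, −0.39 |

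Against the SE, 0.52/1.27 = 0.41 and 0.84/1.27 = 0.66. The third row is missing-not-at-random (MNAR). There the observed-data model overstates benefit by about 0.4, and LOCF is closer to the truth in three of four cases.

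Under random dropout, root mean squared error (RMSE), LOCF vs observed data, is 1.37 vs 1.28 (waned), 1.26 vs 1.28 (constant), 1.28 vs 1.27 (linear) and 1.36 vs 1.30 (late). Power is 65.8% vs 64.5% constant, 55.0% vs 64.2% linear and 49.5% vs 63.7% late. The false-positive rate when the effect has waned is 6.5% vs 5.4%.

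**Binary endpoint.** One carried DO value is 1/12 = 8.3 points of the pooled active rate, or 1/6 = 16.7 points of one dose group. Illustration: true DO rate 60% at weeks 4 and 24, correlation 0.5, and 2 of 12 leave, both with DO at week 4. Observed cases give 0.52 × 0.8 + 0.48 × 0.3 = 56%. LOCF gives 0.167 + 0.833 × 0.56 = 63%. The two bracket the truth.

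**Baseline covariate.** At a single visit, the variance of the adjusted estimate relative to the change score is

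[(1 + rho)/2] × [1 + 1/(N − 4)]

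At rho 0.5 and N = 18 this is 0.75 × 15/14 = 0.80. It equals 1 at rho = (N − 5)/(N − 3): 13/15 = 0.87 for 12 vs 6 and 7/9 = 0.78 for 6 vs 6. Power for a difference of 3.0, without and then with the covariate:

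| rho | 12 vs 6 | 6 vs 6 |
|---|---|---|
| 0.5 | 62% → 71% | 47% → 53% |
| 0.7 | 83% → 86% | 68% → 69% |
| 0.8 | 94.5% → 94.9% | 84.1% → 83.0% |

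**The case against.** The strongest reply is that little depends on this. SAP 7.3 calls efficacy exploratory with nominal p-values, SAP 9.1 tests every visit without singling out week 24, and diary data are listed per participant. Under random dropout the bias is under half an SE and RMSE is nearly equal. All of that stands and limits the point to how the activity signal is read.

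Second, MAR scenarios favour the proposed change. A participant who leaves to seek other treatment may be worsening in a way no recorded visit shows. That also stands: the third row of the simulation shows the observed-data model biased too. A reader might infer that it is unbiased in general; it is not, and an MNAR sensitivity analysis is needed.

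Third, exit procedures include cystometry. A reader might infer that every carried DO value is week 4 standing in for week 24. That holds only when no exit cystometry was done. What remains open is the week to which exit data belong.

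Fourth, baseline is not ignored: it is subtracted, and ANCOVA is named in SAP 9.3. True, but the main model still lacks the covariate. A reader might infer bias from that. Under randomisation there is none, and at high rho there is no gain either.

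Finally, the earlier trial might be read as forecasting unequal dropout here. It used instillation, the times of leaving are not given, and no one left at its higher dose. It shows possibility only.

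**Conclusion.** The point holds in limited form. LOCF is the sole rule for missing efficacy data ahead of a model that can use observed data directly under MAR. The possible bias at later visits runs from about −0.5 to +0.5 voids/day under random dropout, and to about +0.8 if the worst week-8 responders leave. These sizes rest on assumed dropout (2 of 12 active, after week 8), assumed time courses and rho 0.5. With a constant effect, no drift and random dropout there is no bias.

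The observed-data model is the better main analysis for continuous endpoints under MAR and a suitable covariance structure, neither of which the SAP states. If those who would be worst at week 24 leave, it overstates benefit by about 0.4 to 0.5. For DO and response to treatment, the calculation does not show that observed-case analysis is less biased than LOCF, and unweighted GEE itself assumes missing completely at random.

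Leaving out the baseline covariate loses precision when rho is below about 0.87 (12 vs 6) or 0.78 (6 vs 6). The primary safety objective is untouched. The change is worth making because it is cheap and can be settled before the blind is broken.

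**What to change.** **Continuous endpoints (SAP 7.5, 7.7, 9.1).** Fit the mixed model to observed visits, state the MAR assumption and the covariance structure, and add the baseline value of the outcome as a covariate. Analyse early-exit Visit 8 data at the actual study week. Keep LOCF as a labelled sensitivity analysis, and add one simple MNAR analysis that shifts the missing values by a prespecified range of deltas.

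**Binary DO and response to treatment (SAP 7.5, 9.2).** Report observed-case and LOCF results side by side, without claiming that either is less biased. Flag any DO value carried from week 4 because no exit cystometry was done.

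**Cost.** A few SAP sentences, some extra output, no new data, and one degree of freedom for baseline. With a constant effect and random dropout, dropping LOCF as the main rule costs about 1 point of power (65.8% to 64.5%). The covariate costs about 1 point at 6 vs 6 and rho 0.8 (84.1% to 83.0%).

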7.6. Outlier Handling

Potential data entry errors manifested as outliers will be handled following data management process through edit check.

7.7. Adjustments for Covariates

We may use time as a covariate when test certain efficacy endpoints.

8. SUMMARY OF STUDY POPULATION DATA

8.1. Subject Disposition

Subject disposition will be provided for all the subjects in the Safety Population. The total numbers of subjects who received study drug will be displayed in Table 14.1.1. Frequency and percentage of participants who completed study drug per protocol, prematurely discontinued and reasons for discontinuation (adverse event, protocol violation, withdrawal of consent, lost to follow-up, study terminated by sponsor, other reasons) will be tabulated in Table 14.1.1 by treatment group.

Per subject disposition information, eligibility and assignment to analysis population will be displayed in Listings 16.2.1.1, 16.2.1.2, and 16.2.3.

8.2. Protocol Violations

Protocol violations, if any, will be listed in Listing 16.2.1.1. The frequency and percentage of subjects discontinued due to protocol violation will be summarized in Table 14.1.1.

8.3. Demographics and Baseline Characteristics

Descriptive statistics of demographic measurements such as age, sex, ethnicity, race at Screening and measurements of height, weight, and Body Mass Index (BMI) at Visit 1 (Screening Visit) will be summarized for the Safety Population in Table 14.1.2.

Individual subject demographics will be listed in Listing 16.2.4.1. Individual subject baseline medical, surgical history/physical findings displayed in Listings 16.2.4.2. Laboratory test records at screening will be listed with on-treatment laboratory records. Participant OAB history and previous treatment and response to treatment will be detailed in Listings 16.2.4.3 and 16.2.4.4.

